### 8.1. Pharmacokinetic Variables

Plasma concentrations (total and unbound) of DS-3201a will be used to determine the following PK parameters using standard non-compartmental method. Plasma concentration-versus-time data will be summarized using summary statistics by dose/study day/time.

Cycle 1/Days 1 and 2 (Part 1 and Part 2):

- Cmax, Tmax, AUClast
- If appropriate: AUCinf, t1/2, CL/F, Vz/F

Cycle 1/Day 8 (Part 1 and Part 2):

- Cmax, Tmax, AUClast, Cmax and AUClast ratio (d8,d1)
- If appropriate: AUCtau, AUCinf, t1/2, CLss/F, Vss/F

Cycle 1/Days 2, 8, 15, and 22 and Cycle 2/Day 1 (Part 1 and Part 2):

- Ctrough

End-of-treatment (Part 1 and Part 2):

- Ctrough

## **8.2. Pharmacodynamic/Exploratory Biomarker Variables**

### **8.2.1. Pharmacodynamic Biomarker Variables**

- Quantitation of leukemic stem cells in pre- and post-dose bone marrow cells by flow cytometry and/or mass cytometry
- H3K27me3 status in leukemic stem cells in bone marrow and/or blood cells

### **8.2.2. Exploratory Biomarker Analysis**

- Exploratory molecular testing in blood cells and/or bone marrow cells (at pre-dose and post-dose time points)
- Retrospective confirmatory analysis and correlation with pre-therapy cytogenetic and molecular subsets of AML or ALL to response

Optional bone marrow re-biopsy will be performed within 30 days of the last dose of DS-3201b in subjects who have achieved an initial CR/PR to DS-3201b but later developed progressive disease while on therapy.

## 9. SAFETY ASSESSMENTS

### 9.1. Adverse Events

All clinical AEs occurring after the subject signs the ICF and up to 30 ( $\pm 5$ ) days after the last dose of study drug during either Part 1 or Part 2, whether observed by the Investigator or reported by the subject, will be recorded on the AE eCRF page. Medical conditions (including clinical laboratory values/vital signs that are out of range) that were diagnosed or known to exist prior to informed consent will be recorded as part of medical history. All SAEs are to be reported according to the procedures in Section 9.5 SAE Reporting Procedure for Investigators. Always report diagnosis as the AE or SAE term. When a diagnosis is unavailable, report the primary sign or symptom as the AE or SAE term with additional details included in the narrative until the diagnosis becomes available. If the signs and symptoms are distinct and do not suggest a common diagnosis, report them as individual entries of AE or SAE. For events that are serious due to hospitalization, the reason for hospitalization must be reported as the SAE (diagnosis or symptom requiring hospitalization). A procedure is not an AE or SAE, but the reason for the procedure may be an AE or SAE. Pre-planned (prior to signing the ICF) procedure or treatment requiring hospitalization for pre-existing conditions which do not worsen in severity should not be reported as SAEs (see Section 9.4.2 for definitions). For deaths, the underlying or immediate cause of death should always be reported as an SAE. Disease progression is a study endpoint and, consequently, should not be reported as an AE or SAE. However, when a subject dies from disease progression with no other immediate causes, “disease progression” should be reported as an SAE. In addition, any serious, untoward event that may occur subsequent to the reporting period that the Investigator assesses as related to study drug should also be reported and managed as an SAE.

At each visit, the Investigator will determine whether any AEs have occurred by evaluating the subject. Adverse events may be directly observed, reported spontaneously by the subject, or by questioning the subject at each study visit. Subjects should be questioned in a general way, without asking about the occurrence of any specific symptoms. All clinical laboratory values must be appraised by the Investigator as to clinical significance. All post-baseline abnormal clinical laboratory values considered clinically significant by the Investigator must be recorded as an AE on the eCRF, and if serious, reported as an SAE following the procedures in Section 9.5.

Investigator should follow subjects with AEs until the event has resolved or the condition has stabilized. In case of unresolved AEs including significant abnormal clinical laboratory values at the EOT assessment, these events will be followed-up until resolution or until they become clinically not relevant.

### 9.2. Safety Endpoints

Safety endpoints will include incidence of AEs, SAEs, TEAEs, DLTs, physical examination findings (including ECOG-PS), vital sign measurements, standard clinical laboratory parameters, histamine level in plasma, and ECG parameters.

## **9.3. Adverse Events of Special Interest**

Differentiation syndrome is an adverse event of special interest (AESI) for DS3201-A-U102 and as of 18 Jan 2020, it has been reported in 1 subject with AML.

When subjects with acute leukemia are treated with DS-3201b, vigilance should be exercised in while monitoring them for development of possible differentiation syndrome. It is important to both promptly recognize the signs and symptoms of differentiation syndrome and implement prompt management.

## **9.4. Definitions**

### **9.4.1. Adverse Event**

An AE is defined as any untoward medical occurrence in a subject or clinical investigation subject administered a pharmaceutical product and which does not necessarily have to have a causal relationship with this treatment. An AE can therefore be any unfavorable and unintended sign (including an abnormal clinical laboratory finding, for example), symptom, or disease temporally associated with the use of a medicinal product, whether or not considered related to the medicinal product (ICH E2A Guideline. Clinical Safety Data Management: Definitions and Standards for Expedited Reporting, Oct 1994).

It is the responsibility of Investigators, based on their knowledge and experience, to determine those circumstances or abnormal clinical laboratory findings that should be considered AEs.

### **9.4.2. Serious Adverse Event**

Any untoward medical occurrence that at any dose:

- Results in death
- Is life-threatening
- Requires inpatient hospitalization or prolongation of existing hospitalization
- Results in persistent or significant disability/incapacity
- Is a congenital anomaly/birth defect
- Is an important medical event

Note: The term “life-threatening” in the definition of “serious” refers to an event in which the subject was at risk of death at the time of the event; it does not refer to an event which hypothetically might have caused death if it were more severe (ICH E2A Guideline. Clinical Safety Data Management: Definitions and Standards for Expedited Reporting, October 1994).

Medical and scientific judgment should be exercised in deciding whether expedited reporting is appropriate in other situations, such as important medical events that may not be immediately life-threatening or result in death or hospitalization, but may jeopardize the subject or may require intervention to prevent one of the other outcomes listed in the definition above.

Examples include allergic bronchospasm, convulsions, and blood dyscrasias, or development of drug dependency or drug abuse.

Note:

- A procedure is not an AE or SAE, but the reason for the procedure may be an AE or SAE.
- Pre-planned (prior to signing the ICF) procedures or treatment requiring hospitalizations for pre-existing conditions that do not worsen in severity are not SAEs.

#### **9.4.3. Adverse Event Severity**

All AEs will be graded (1 to 5; see below) according to the NCI-CTCAE, Version 4:

- Grade 1 Mild AE
- Grade 2 Moderate AE
- Grade 3 Severe AE
- Grade 4 Life-threatening or disabling AE
- Grade 5 Death related to AE

Severity vs. Seriousness: Severity is used to describe the intensity of a specific event while the event itself, however, may be of relatively minor medical significance (such as severe headache). This is not the same as “seriousness,” which is a universal and global regulatory definition based on subject/event outcome at the time of the event. For example, the NCI-CTCAE Grade 4 (life-threatening or disabling AE) is assessed based on unique clinical descriptions of severity for each AE, and these criteria may be different from those used for the assessment of AE seriousness. An AE assessed as Grade 4 based on the NCI-CTCAE grades may or may not be assessed as serious based on the seriousness criteria. For example, an event of headache may be classified moderate by an Investigator, but upon presentation to a medical facility, subject is admitted overnight for observation upgrading this report to serious based upon international regulatory definition.

#### **9.4.4. Causality Assessment**

The Investigator should assess causal relationship between an AE and DS-3201b on the basis of his/her clinical judgment and the following definitions. The causality assessment should be made based on the available information and can be updated as new information becomes available.

- 1 = Related:
  - The AE follows a reasonable temporal sequence from study drug administration, and cannot be reasonably explained by the subject’s clinical state or other factors (eg, disease under study, concurrent diseases, and concomitant medications).
  - The AE follows a reasonable temporal sequence from study drug administration, and is a known reaction to the drug under study or its chemical group, or is predicted by known pharmacology.
- 2 = Not Related:

- The AE does not follow a reasonable sequence from study drug administration, or can be reasonably explained by the subject's clinical state or other factors (eg, disease under study, concurrent diseases, and concomitant medications).

#### **9.4.5. Action Taken Regarding the Study Drug**

- 1 = None: No change in study drug dosage was made.
- 2 = Discontinued Permanently: The study drug was permanently stopped.
- 3 = Reduced: The dosage of study drug was reduced.
- 4 = Interrupted: The study drug was temporarily stopped.
- 5 = Increased: The dosage of study drug was increased.

#### **9.4.6. Adverse Event Outcome**

- 1 = Recovered/Resolved
  - The subject fully recovered from the AE with no residual effect observed.
- 2 = Recovered/Resolved with Sequelae
  - The residual effects of the AE are still present and observable.
  - Identify sequelae/residual effects.
- 3 = Not Recovered/Not Resolved
  - The AE itself is still present and observable.
- 4 = Fatal
- 5 = Unknown

#### **9.4.7. Other Action Taken for Event**

- 1 = None
  - No treatment was required.
- 2 = Medication required
  - Prescription and/or over-the-counter medication was required to treat the AE.
- 3 = Hospitalization or prolongation of hospitalization required
  - Hospitalization was required or prolonged due to the AE, whether or not medication was required.
- 4 = Other

## **9.5. Serious Adverse Event Reporting Procedure for Investigators**

### **9.5.1. Initial Reports**

Within 24 hours of receipt of an SAE report:

- Complete a Daiichi Sankyo Serious Adverse Event Report (SAVER) form, sign it, and fax it to the CRO using the designated fax transmittal form. The CRO will review and forward the SAVER form to Daiichi Sankyo Clinical Safety and Pharmacovigilance (CSPV).
- Call the CRO SAE hotline for any questions regarding SAE reporting.
- Place the initial version of SAVER in the subject's file.

### **9.5.2. Follow-up Reports**

This is NEW information received on a previously reported SAE that is clinically significant.

Within 24 hours of the receipt of new information for a clinically significant reported SAE:

- Complete a Daiichi Sankyo SAVER form with the new information. Please complete Sections 1 through 3 even if they contain no new information. For Sections 4 through 10, provide only the new information. Sign and fax the form to the CRO using the fax transmittal form.
- For SAEs that resulted in death, provide the autopsy report via e-mail, fax, or express mail.
- The CRO will review and forward the follow-up SAVER form and supporting documents to Daiichi Sankyo CSPV PPD.
- Place the follow-up version of the SAVER form and all supporting documentation in the subject's file.

### **9.5.3. Notifying Regulatory Authorities, Investigators, and IRBs**

Daiichi Sankyo and/or CRO will inform Investigators and regulatory authorities of any Suspected Unexpected Serious Adverse Event Reactions (SUSARs) occurring in other study centers or other Daiichi Sankyo studies of the investigational product, as appropriate per local reporting requirements.

In the United States, it is the Investigator's responsibility to inform the IRB upon receipt of the Sponsor's notification of SUSARs that occurred with the investigational product.

## **9.6. Exposure In Utero During Clinical Studies**

Daiichi Sankyo must be notified of any subject who becomes pregnant while receiving study drug or up to 30 ( $\pm$  2) days after the last administration of study drug. Although pregnancy is not technically an AE, all pregnancies must be followed to conclusion to determine their outcome. This information is important for both drug safety and public health concerns. It is the responsibility of the Investigator, or designee, to report any pregnancy in a subject using the Exposure In Utero (EIU) Reporting form. Please contact your study monitor to receive the EIU

Reporting Form upon learning of a pregnancy. The Investigator should make every effort to follow the subject until completion of the pregnancy. If the outcome of the pregnancy meets the criteria for immediate classification as an SAE (ie, post-partum complications, spontaneous abortion, stillbirth, neonatal death, or congenital anomaly, including that in an aborted fetus), the Investigator should follow the procedures for reporting SAEs as outlined in Section 9.5.

The potential for DS-3201b to affect fertility and embryo-fetal development has not been tested. Women of childbearing potential should be informed of the potential risk, have periodic pregnancy tests, and use highly effective methods of birth control during treatment and for an additional 90 days after the end of treatment. Women should not breastfeed during the study and for an additional 90 days after the end of treatment.

The potential of DS-3201b to be transferred by semen and its effect on sperm is unknown. Male subjects with partners of childbearing potential should inform their partners of their participation in the clinical study and use highly effective methods of birth control during treatment and for an additional 90 days after the end of treatment.

Additional information can be found in the Investigator's Brochure.

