- 8. Women of childbearing potential and their partner must agree to use an adequate method of contraception during the study and until 3 months after the last treatment, and must not retrieve ova or donate from the time of screening and throughout the study treatment period and for  $\geq 3$  months after the final dose of study drug. Males and their partner must be surgically or biologically sterile or agree to use an adequate method of contraception during the study until 3 months after the last treatment, and must not freeze or donate sperm starting at screening and throughout the study period and for  $\geq 3$  months after the final dose of study drug (see Section 17.7).
- 9. Is willing to provide bone marrow biopsies and comply with evaluations as requested by protocol.
- 10. Has a life expectancy of at least 3 months.

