## 17.7. Highly Effective Methods of Birth Control

Female subjects of reproductive/childbearing potential with a male sexual partner must agree to use a highly effective form of contraception or avoid intercourse during and upon completion of the study and for at least 3 months after the last dose of study drug. For the purpose of this protocol, methods considered as highly effective birth control include:

- a. Combined (estrogen- and progestogen-containing) hormonal contraception associated with inhibition of ovulation (oral, intravaginal, or transdermal delivery).
- b. Progestogen-only hormonal contraception associated with inhibition of ovulation (oral, injectable, or implantable delivery).
- c. Intrauterine device (IUD).
- d. Intrauterine hormone-releasing system (IUS).
- e. Bilateral tubal occlusion.
- f. Vasectomized partner.
- g. Complete sexual abstinence.

Non-childbearing potential is defined as pre-menopausal with documented tubal ligation or hysterectomy; OR postmenopausal with documented  $\geq 12$  months of spontaneous amenorrhea (in questionable cases, a blood sample with simultaneous follicle-stimulating hormone [FSH]  $>40$  mIU/mL and estradiol  $<40$  pg/mL [ $<140$  pmol/L] is confirmatory). Females on hormone replacement therapy (HRT) and whose menopausal status is in doubt will be required to use one of the contraception methods outlined above for women of childbearing potential if they wish to continue their HRT during the study. Otherwise, they must discontinue HRT to allow confirmation of post-menopausal status prior to study enrollment. For most forms of HRT, at least 2 to 4 weeks must elapse between the cessation of therapy and the blood draw; this interval depends on the type and dosage of HRT. Following confirmation of their post-menopausal status, they can resume use of HRT during the study without use of a contraceptive method.

Female subjects must not retrieve ova or donate from the time of screening and throughout the study treatment period, and for  $\geq 3$  months after the final dose of study drug.

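### The explicit pregnancy notification rule stops 30 (±2) days after the last dose, about 60 days before the protocol's own 90-day contraception period ends

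*Combined protocol and SAP*

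**What the plan says.** Section 9.6 states the notification rule. The sponsor has to hear about a subject "who becomes pregnant while receiving study drug or up to 30" days, with a tolerance of 2 days either way, counted from the final dose. It then says that every pregnancy is to be tracked to its outcome and that the Investigator must submit an Exposure In Utero (EIU) form. Neither of those two statements carries a time limit of its own.

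The same section says that effects on fertility and on the embryo and fetus have not been tested. It tells women of childbearing potential, and men with partners of childbearing potential, to "use highly effective methods of birth control during treatment and for an additional 90 days after the end of treatment". On breastfeeding it says: "Women should not breastfeed during the study and for an additional 90 days after the end of treatment".

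The longer period is repeated elsewhere. Under inclusion criterion 8 (Section 4.1.1), women of childbearing potential and their partners "must agree to use an adequate method of contraception during the study and until 3 months after the last treatment". Section 17.7 asks female subjects for highly effective contraception or abstinence "for at least 3 months after the last dose of study drug".

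**The concern.** Two post-treatment windows in one section do not match. Subjects are asked to avoid pregnancy for 90 days, yet the only sentence that dates the reporting duty ends at 30 days. A site that applies the dated rule literally would have no stated obligation to tell the sponsor about a conception on, say, day 60, although preventing that event is the purpose of the contraception rule.

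What is at stake is safety information. Section 9.6 itself gives drug safety and public health as reasons for following pregnancies. For a compound with no reproductive data, each case carries information, and a case that is not notified cannot be followed to its outcome.

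**Working it through.** The plan gives no figure on this point to reproduce. The check compares the windows and then looks for any other provision that would close the gap.

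**Inputs**
- Notification window: 30 (±2) days after the last administration (Section 9.6).
- Contraception and breastfeeding period: 90 days after the end of treatment (Section 9.6); 3 months in inclusion criterion 8 and Section 17.7.
- Assumptions: 3 months is taken as 90 days, and the end of treatment as the date of the last dose.

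**Length of the gap** = contraception period − notification window

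| Notification window (days) | Gap (days) | Share of the 90 days |
|---|---|---|
| 28 | 90 − 28 = 62 | 62/90 = 68.9% |
| 30 | 90 − 30 = 60 | 60/90 = 66.7% |
| 32 | 90 − 32 = 58 | 58/90 = 64.4% |

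The gap opens between day 29 and day 33, depending on the tolerance, and closes at day 90.

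**Does another provision cover days 31 to 90?**
- *Pregnancy tests.* The last scheduled test is at the end-of-treatment visit (footnote c of Tables 17.2 and 17.3), which takes place within 30 days of the last dose (Sections 6.3.1.10 and 6.3.2.11).
- *Adverse event collection.* Routine collection ends at 30 (±5) days (Section 9.1). Section 9.6 also says that a pregnancy is not, strictly, an adverse event.
- *Late serious events.* Section 9.1 requires later reporting of a serious event that the Investigator judges related to study drug. This could catch a bad pregnancy outcome after a relatedness judgment, but not the pregnancy itself.
- *Long-term follow-up.* Section 6.4 and footnotes q and r of Tables 17.2 and 17.3 list later leukemia treatment, transplant information, response and survival. Pregnancy is not listed.
- *Undated sentences in Section 9.6.* They follow the dated sentence and can be read either as procedure for cases inside the 30 days or as a general duty. The text does not settle which.

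**Could the existing calls carry the question?** The end-of-study contact is at 30 (±5) days and the calls are every 3 months after it. The first call therefore falls at about 30 + 90 = 120 days (115 to 125 with the ±5 days), after day 90. A single question at that call would look back over the whole gap.

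**The case against.** The strongest reply has four parts.

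1. *The section does not forbid later reports.* Its sentences on following pregnancies and submitting the form have no time limit, and late serious outcomes judged related are reportable under Section 9.1. This stands in part. A reader might infer that pregnancies in days 31 to 90 will go uncollected. The documents do not support that; they support only that no explicit requirement covers those days. The ambiguity still needs resolving, because the only dated sentence says 30 days.

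2. *A contraception margin is not an exposure period.* This stands. A reader might infer that the protocol regards a conception on days 31 to 90 as drug-exposed. It never says so. It sets a 90-day precaution without giving a rationale for its length, and the only half-lives it states are from animals (2.29 to 7.14 hours in rats and 1.73 to 5.88 hours in dogs, Section 1.1.1.5.3). The 30 days may be a deliberate match to adverse event collection. If so, the protocol does not explain why reporting should stop before the precaution does.

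3. *Events will be very few.* This also stands. Section 11.10 expects 21 or more subjects in escalation and about 40 at the expansion dose, some of whom come from escalation. Contraception is required throughout the period, and Section 1.2 cites a median survival of 3.8 months in AML refractory to induction. The two-thirds figure is a share of calendar days and says nothing about the share of pregnancies missed.

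4. *Changing one sentence would not collect the data.* This is correct for active collection, because the follow-up calls do not now ask about pregnancy. The fix has to cover both.

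**Conclusion.** The mismatch is real and can be read from Section 9.6 alone. The dated notification rule ends about 60 days (58 to 62) before the contraception period that the same section, inclusion criterion 8 and Section 17.7 set. No scheduled test, adverse event rule or listed follow-up item closes the gap. The conclusion rests on treating 3 months as 90 days and on reading the undated sentences as ambiguous rather than as a clear open-ended duty. If the sponsor did intend an open-ended duty, the 30-day limit conflicts with it and the section still needs correcting.

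The consequence is limited to the completeness of reproductive safety data. No endpoint, analysis set, sample size or dose decision depends on this window. It is a cheap improvement of minor priority.

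**What to change.** Reconcile the passages in two places.

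- *Section 9.6:* extend the notification window from 30 (±2) days to the 90-day (3-month) period the protocol already uses, and state that the follow-up and EIU form sentences apply to that same window.
- *Section 6.4 and footnotes q and r of Tables 17.2 and 17.3:* add a question, for subjects of childbearing potential, on any pregnancy since the last contact, asked at the first 3-monthly call. A conception near day 90 might not be recognised by then; repeating the question at the next call would cover it.

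The cost is a short amendment, one extra telephone question with its data field, and probably only a few more EIU forms. The form and the calls already exist, so no new visit or test is needed.
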